### **10.2.2.2 Assessment of Intensity**

Each adverse event will be graded according to the following definitions:

- **Mild:** asymptomatic or mild symptoms; clinical or diagnostic observations only; intervention not indicated;
- **Moderate:** minimal, local or noninvasive intervention indicated; limiting age-appropriate instrumental activities of daily living (ADL)  
[Instrumental ADL refer to preparing meals, shopping for groceries or clothes, using the telephone, managing money, etc];
- **Severe:** medically significant but not immediately life-threatening; hospitalization or prolongation of hospitalization indicated; disabling; limiting self-care ADL [self-care ADL refer to bathing, dressing and undressing, feeding self, using the toilet, taking medications, and not bedridden]

### **10.2.2.3 Relationship to Study Drug**

The assessment of the relationship of an AE to the administration of study drug is a clinical decision based on all available information at the time of the completion of the CRF.

The causal relationship of the study drug to an AE will be rated as follows:

- **Related:** The AE has at least a possible or stronger causal relationship to the study drug, i.e., there are facts in evidence to suggest a causal relationship to the study drug. The study treatment and the AE are reasonably related in time, and any alternative etiology is equally or less likely.

- **NOT Related:** Exposure to study treatment did not occur; or the occurrence of the AE is not reasonably related in time, or is due to an underlying/interventient illness, or to other medication or procedure; or the AE is considered unlikely to be related to the study treatment.

#### **10.2.2.4 Action Taken**

The action taken toward the study drug in response to an AE will be listed as one of the following:

- **None:** No change in study drug dosage was made.
- **Reduced:** Dose of study drug was reduced, with or without a period of temporary suspension of dosing.
- **Discontinued:** The study drug was permanently stopped.

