## 4.6 Dose Adjustments / Toxicity Management

Adverse events will be graded for intensity by the investigator (see [Section 10.2.2.2](#)).

Dosing will be discontinued for all study drug-related SAEs.

A member of the study staff will contact any subject who is suspected of experiencing neuropsychiatric AEs to determine the need for an unscheduled visit before further dose escalation may proceed. Subjects who are experiencing any AEs may also be asked to return for an unscheduled visit. Subjects who are suspected of experiencing a neuropsychiatric event should be seen in person.

In all subjects with intolerable AEs (as defined in [Section 10.2.1](#)) that are considered related to study drug, treatment should be suspended for up to 48 hours or until the AE resolves to a tolerable level of severity, whichever is earlier. In subjects who are unable to tolerate 6 mg BID, 8 mg BID or 10 mg BID, dosing may then be resumed at a previously tolerated lower dose. Only a single dose-step reduction (i.e., 10 mg BID to 8 mg BID, 8 mg BID to 6 mg BID, or 6 mg BID to 4 mg BID) is permitted. Reescalation of the dose is NOT permitted. Dosing should be discontinued if there is recurrence of intolerable AEs after the dose reduction. Subjects who experience intolerable AEs while receiving the 2 mg BID or 4 mg BID dose will be discontinued from treatment. Table 2 details dose reductions by dose level.

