**Table 2 Study Drug Dose Reduction for Intolerable AEs**

Dose and Schedule of Study Drug	Dose Reduction
2 mg BID	Remove from treatment 
4 mg BID	Remove from treatment
6 mg BID	4 mg BID
8 mg BID	6 mg BID
10 mg BID	8 mg BID

1 – Subjects who are removed from treatment for AE(s) should be followed for resolution of the AE(s) and should complete all assessments scheduled for the End-of Study (EOS)/Follow-up (FU) Visit, as well as all assessments that they are capable of completing on the scheduled visit day if the decision to remove from treatment is made on a scheduled visit day. Likewise, if the investigator plans to temporarily interrupt dosing because of an AE and the decision is made on a scheduled visit day, then the subject should complete all scheduled assessments that they are capable of completing on the visit day on which they appear.

All subjects who discontinue treatment due to AEs will be followed for AE outcome. All AEs should be followed for resolution or for 30 days from the last dose of study drug, whichever is shorter.

The Study Safety Representative should be notified of all dose reductions as soon as is feasible.

All subjects who discontinue treatment due to AEs will be followed for AE outcome. All AEs should be followed for resolution or for 30 days from the last dose of study drug, whichever is shorter.

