3.3.7. Definitions and Terminology

Age

The age of a subject is defined as the number of whole years between the subject's birth date and the date of informed consent.

Day 1 (Baseline)

Day 1 is the earliest day that study drug is initiated.

Study Day

Study Day is defined relative to Day 1 as follows: Study Day = Date of event – Date of Day 1 +1*(1 if date of event \geq Date of Day 1, 0 otherwise).

Study Visit

Study Visit is the nominal visit as recorded on the eCRF.

Baseline Value

For purposes of analysis, the baseline value is defined as the last non-missing value obtained prior to initiation of study drug.

Change from Baseline

Change from baseline for a given endpoint is defined as the Study Day X value minus the baseline value.

Percent Change from Baseline

Percent change from baseline for a given endpoint is defined as the Study Day X value minus the baseline value, quantity divided by the baseline value, multiplied by 100.

$$\text{Percent Change from Baseline} = (\text{Study Day X} - \text{Baseline})/\text{Baseline} * 100$$

Days on Study

Days on study is defined as the number of days from the date of study drug initiation to the final study visit (includes in home or in clinic assessments).

Completer

A subject is defined as a completer if he/she completes the Day 26 EEG and Day 27 dosing regardless of completing the Day 33 visit.

Treatment Period

The treatment period is the period during which a subject receives study drug (i.e., first dose through Day 27).

Days on Study Drug

Days on study drug is defined as the number of days in the treatment period. The date of the last dose of study drug as recorded on the End of Study Visit form or from the AICure electronic data transfer.

Total Study Drug Expected (capsules)

The total study drug expected is defined as the total number of capsules expected to be taken as recorded from all sources and reported from the AICure system.

Total Study Drug Received (capsules)

The total study drug received is defined as the total number capsules of taken as recorded from all sources and reported from the AICure system.

Total Study Drug Received (mg)

The total study drug received (mg) amount will be multiplied by 2 for subjects receiving CX-8998 to calculate the amount of study drug received in mg (i.e., each capsule is 2 mg).

Treatment Compliance

Treatment compliance will be calculated for each subject as a percentage using the following formula:

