5.1. SUBJECT DISPOSITION, DEMOGRAPHIC AND BASELINE CHARACTERISTICS, AND EXTENT OF EXPOSURE

Subject disposition will be presented for all enrolled subjects. The number of subjects enrolled will be presented for each study population and site. The number of subjects who completed the study and discontinued from the study will be provided. The primary reasons for discontinuation from the study at any point also will be presented. Days on study will be summarized.

Demographic data and baseline characteristics including age, gender, race, ethnicity, height, weight will be summarized using descriptive statistics for the ITT population.

Extent of exposure will be summarized for the safety population using the following measures: days on study drug and total study drug received (in mg), as estimated by the number of capsules dispensed and returned. Treatment compliance also will be summarized. The number and percentage of subjects requiring a dose reduction will be summarized.

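### A dose interruption for an adverse event that resumes at the same dose has no action-taken code and no planned count, and the paused days still count as days on study drug

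*Protocol*

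**What the plan says.** Protocol 10.2.2.4 sets up a closed list: "The action taken toward the study drug in response to an AE will be listed as one of the following". There are three codes:

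- None, for an unaltered dose: "No change in study drug dosage was made".
- Reduced, which takes in a suspension only when the dose also comes down: "Dose of study drug was reduced, with or without a period of temporary suspension of dosing".
- Discontinued, for a permanent stop.

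Two parts of the protocol deal with pauses. Section 4.6 covers intolerable AEs judged related to study drug, for which "treatment should be suspended for up to 48 hours", or less if the event becomes tolerable sooner. Footnote 1 to Table 2, repeated in section 6.4.1, is more general. It says which visit assessments to complete "if the investigator plans to temporarily interrupt dosing because of an AE", and it does not require the AE to be intolerable or related, or the dose to be reduced afterwards.

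On reporting, SAP 5.1 states: "The number and percentage of subjects requiring a dose reduction will be summarized". SAP 5.3.2.3 and Table 14.3.2.2 cover treatment-emergent events that lead to stopping the drug. SAP 3.3.7 states: "Days on study drug is defined as the number of days in the treatment period", and there the treatment period runs from first dose through Day 27. SAP 5.1 and Table 14.1.4 also report total milligrams received and percent compliance. Listings 16.2.5.1 (dose change log), 16.2.5.2 (AICure compliance) and 16.2.7 (adverse events) are planned by subject.

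**The concern.** Safety and tolerability are the primary objective of this single-arm titration study. How often an AE forces a change in dosing is direct evidence on that objective. The protocol acknowledges three such changes (interruption, reduction, permanent stop), but it gives codes to only two, and the SAP reports only those two.

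Two separate gaps follow. In recording, a same-dose interruption would enter the AE record as no change, and that record could then disagree with the dose change log. In reporting, no planned table has a place for interruptions however they are coded. A reader of the study report could not tell how many subjects needed a pause because of an AE. Days on study drug would also look the same for a subject who paused and one who did not.

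**Working it through.** **Step 1: fit each pathway to a code.** The documents give no figure to reproduce here, so the first check sets the text side by side.

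| Pathway | Where described | Code that fits |
|---|---|---|
| Related intolerable AE at 6, 8 or 10 mg BID: suspend, then resume one step lower | Protocol 4.6, Table 2 | Reduced |
| Related intolerable AE at 2 or 4 mg BID | Protocol 4.6, Table 2 | Discontinued |
| Interruption for any AE, then restart at the same dose | Interruption foreseen in Protocol 6.4.1 and Table 2 footnote 1; restart dose not stated | Not Reduced (dose unchanged), not Discontinued (not permanent); only None remains |

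**Step 2: trace a same-dose pause through the SAP measures.**

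- Dose-reduction count (5.1): no effect.
- Events leading to discontinuation (Table 14.3.2.2): no effect.
- Days on study drug (3.3.7): no effect, because the paused days lie inside the treatment period.
- Total milligrams received: falls, because it is built from capsules taken.
- Compliance: falls if expected capsules are not lowered for the pause. The SAP does not say whether they are.
- Tables of treatment-emergent events and Listing 16.2.7: the AE still appears, without a link to the pause.

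**Step 3: size one pause.** Capsules per step = days × 2 × capsules per dose, at 2 mg per capsule.

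- Protocol 4.3, Days 1–26: 2×2×1 + 6×2×2 + 6×2×3 + 6×2×4 + 6×2×5 = 4 + 24 + 36 + 48 + 60 = 172 capsules = 344 mg.
- SAP 1.1, adding the Day 27 morning dose: 172 + 5 = 177 capsules = 354 mg.
- Protocol Table 3 note 20, with the last dose on the morning of Day 26: 172 − 5 = 167 capsules = 334 mg.

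Assume a pause of 48 hours. That length is borrowed from section 4.6, since the footnote and 6.4.1 state none. Assume also that the pause falls within one dose step and the titration calendar does not shift. Four doses are then missed.

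| Dose at pause | Missed | Share of 344 mg | Share of 354 mg | Compliance on 177 capsules, expected count unchanged |
|---|---|---|---|---|
| 4 mg BID | 8 capsules, 16 mg | 4.7% | 4.5% | 95.5% |
| 6 mg BID | 12 capsules, 24 mg | 7.0% | 6.8% | 93.2% |
| 8 mg BID | 16 capsules, 32 mg | 9.3% | 9.0% | 91.0% |
| 10 mg BID | 20 capsules, 40 mg | 11.6% | 11.3% | 88.7% |

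On the 334 mg schedule the 10 mg row is 40/334 = 12.0%, with compliance of 88.0%.

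Days on study drug stays at 27 for a subject who completes the SAP schedule. If the four missed doses fill two calendar days, dosing took place on 27 − 2 = 25 days. If the pause starts with an evening dose, only one day is wholly without drug and the figure is 26.

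**Step 4: weight of one subject.** 1/15 = 6.7 percentage points.

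**The case against.** The strongest reply is that little is lost. Total milligrams received does register the pause: at 10 mg BID it drops from 354 to 314 mg on the SAP schedule. Compliance may register it too. The AE remains in the tables by severity, relationship and dose, and the gap may be visible in the dosing listings. The suspension rule that the protocol spells out in section 4.6 is described as ending in a lower dose or in discontinuation, and both have codes. The definition of an intolerable AE is broad enough to take in mild or moderate related events that make the subject want to stop. What remains rests on one sentence about visit assessments, which sets out no same-dose restart. The eCRF is not among the documents. SAP 1.1 says the data are presented under protocol amendment 3, whose code list is not shown. And no planned table uses the None code.

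Most of this stands, and it sets the limits of the point. It does not remove it. The general interruption wording appears twice and does not require a reduction. A lower milligram total or compliance figure cannot separate a pause for an AE from forgotten capsules. That the None code feeds no table means only that the reporting gap would exist even with correct coding.

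A reader might go further and infer that interruptions vanish from the tolerability and exposure results altogether, that section 4.6 suspensions are uncoded, or that interruption is the commonest dose action. The first two are contradicted by the provisions just described. Nothing in the documents speaks to the third.

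**Conclusion.** The point holds as a limited recording and reporting gap. An interruption for an AE that resumes at the same dose has no code of its own in Protocol 10.2.2.4. By elimination it would be coded as no change, which is untrue. No SAP table counts such interruptions or links them to the AE, and days on study drug includes the paused days. Exposure as a whole is not lost, and the AE itself is still reported.

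Each affected subject is 6.7 percentage points of 15. One 48-hour pause at 10 mg BID is 40 mg: 11.6% of the protocol's 344 mg, or 11.3% of the SAP's 354 mg. It overstates days on study drug by one or two days out of 27.

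This rests on three assumptions: that the eCRF follows the protocol's list, that same-dose restarts occur, and that a pause lasts 48 hours. How many subjects would be affected cannot be judged from the documents.

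**What to change.** - **Protocol 10.2.2.4 and the AE CRF:** add a fourth code, *Interrupted: dosing temporarily suspended and resumed without dose reduction*.
- **Data already collected:** derive a flag for AE-driven interruption from the dose change log, the dosing records and the AE dates. This part can still change what is reported, because the data are presented under amendment 3 and a new code would not reach them.
- **SAP 5.1 and Table 14.1.4:** report the number and percentage of subjects with such an interruption beside dose reductions.
- **SAP 3.3.7:** report days on study drug net of days with no dose taken, and state whether expected capsules are lowered during a directed pause.

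The cost is one CRF code, one table row and a little more programming. The tolerability figure may look slightly less favourable. Sample size and the other analyses are unaffected, and no dosing rule changes.

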#### **10.2.2.5 Outcome of Adverse Event**

The outcome of an AE will be recorded as one of the following:

- **Recovered:** fully recovered or the condition has returned to the level observed at baseline
- **Recovered with sequelae:** resulted in persistent or significant disability or incapacity; the nature of the sequelae should be specified
- **Not yet recovered**
- **Death**

#### **10.2.3 Adverse Event Follow-up**

Adverse events requiring therapy must be treated with recognized standards of medical care to protect the health and well-being of the subject.

Any subject who has any AE (whether serious or non-serious) or clinically significant (in the investigator's opinion) abnormal laboratory test values will be evaluated by the investigator or qualified designee and will be treated and followed up until the symptoms or values return to normal or acceptable levels, as judged by the investigator and the sponsor.

All AEs, whether serious or non-serious, will be collected beginning at the time the ICF is signed through the telephone safety check on Day 33. All AEs should be followed until resolution or:

1. 30 days from onset; or
2. 30 days after the last dose of study drug; or
3. the subject is lost to follow-up (as defined in [Section 6.4.1](#)); or
4. the subject withdraws consent,

whichever occurs first.

SAEs will be reported up to 30 days after the last dose of study drug. A follow-up phone call will be made 30 days after the last dose of study drug for evaluation of any SAEs.

Any follow-up information available at the time of the subject's end of study will be included in the clinical study report.

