    - v. For other ECG findings (e.g., including, but not necessarily limited to, tachycardia, bundle branch block, frequent ectopic beats) the investigator should send a scanned, identity-blinded copy of the ECG tracing to the Study Safety Representative for review.
- 10) Positive result for human immunodeficiency virus (HIV), hepatitis B [indicating ongoing infection], or hepatitis C at screening or otherwise known ongoing infection with HIV, hepatitis B, or hepatitis C, unless curative therapy has been completed; for hepatitis C curative therapy is defined as negative polymerase chain reaction (PCR) for hepatitis C virus (HCV) RNA.
- 11) Significant hepatic (AST/ALT or bilirubin  $\geq$ 2  $\times$  ULN) or renal disease (creatinine clearance  $\leq$ 39 mL/min).
- 12) History of alcohol or substance abuse within the last year.
- 13) A current C-SSRS score of 4 or 5 at screening or history of suicide attempt.
- 14) Psychological, social, familial, or geographical reasons that would hinder or prevent compliance with the requirements of the protocol or compromise the informed consent process.

- 15) Any other condition and/or situation that causes the investigator or Study Safety Representative to deem a subject unsuitable for the study (including, but not limited to, expected study medication noncompliance, inability to medically tolerate the study procedures, or a subject's unwillingness to comply with study-related procedures)
- 16) Treatment with an investigational agent within 30 days prior to the first dose of CX-8998 or planning to receive an investigational agent during the study.
- 17) Subjects who do not experience a provoked absence seizure during either HV period and who have fewer than 3 typical absence seizures during the baseline video-EEG (considered to be screen failures).

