### **6.4.1 Follow-up Procedures for Subjects Who Withdraw/Discontinue Prematurely**

If a subject withdraws from the study, attempts should be made to contact the subject to determine the reason(s) for discontinuation. If a subject does not return to the clinic for follow-up visits, attempts should be made to contact the subject via phone, email, or mail. At least 3 documented attempts (one of which should be a certified letter) should be made to contact the subject before declaring a subject lost to follow-up. The Study Safety Representative must be informed as soon as possible if a subject discontinues or withdraws early.

The date and the reason for study drug discontinuation or subject withdrawal from the study must be recorded on the case report form (CRF). In case of early discontinuation or withdrawal of a subject, every effort must be made to report all study-mandated observations up to the time of discontinuation/withdrawal as completely as possible.

Subjects who are removed from treatment for AE(s) should be followed for resolution of the AE(s) (see [Section 10.2.3](#)) and should complete all assessments scheduled for the End-of-Study (EOS) Visit, as well as all assessments that they are capable of completing on the scheduled visit day if the decision to remove from treatment is made on a scheduled visit day. Likewise, if the investigator plans to temporarily interrupt dosing because of an AE and the decision is made on a scheduled visit day, the subject should complete all scheduled assessments that they are capable of completing on the visit day on which they appear.

If the reason for discontinuation/withdrawal is medical and the subject has not withdrawn consent, the subject should remain under the supervision of the investigator until the medical issue is resolved or otherwise declared stable.

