14. On Day 1, PK samples will be taken at time 0 (predose; before subject takes first dose of study drug in the clinic) and at 1, 2, and 4 hours after administration of study drug. Two postdose PK samples, separated by >2 hours, will be obtained on Day 26. The time of the last dose of study drug and the time of the blood draw will be recorded.
15. A standard multi-lead 6.5-hour video EEG will be obtained using HV and PS. The first 30 minutes will consist of HV and PS. For HV, subjects will be hyperventilated for 5 minutes or until the subject has an absence seizure (HV period 1). If no absence seizure occurs during HV period 1, the subject will rest for 5 minutes and then perform hyperventilation for an additional 5 minutes (HV period 2). Photic stimulation will be performed as described in the EEG charter. The EEG will be centrally evaluated by a qualified rater.
16. After completion of the above 30-minute video-EEG during which HV and PS are conducted, the video-EEG will continue, and the subjects will be monitored during wakefulness for an additional 6 hours. The EEG recording will be centrally evaluated by a qualified rater.
17. The “Lifetime” version of the C-SSRS will be used at screening, and the “Since Last Visit” version will be completed at all other visits.
18. The UM-PDHQ is a 20-item clinician-administered questionnaire that quantitatively and qualitatively assesses hallucinations. The UM-PDHQ will be completed for any subject who reports hallucinations.
19. All AEs, irrespective of the relatedness to the study drug, will be captured from the time the ICF is signed through the EOS visit. All AEs should be followed until resolution, for 30 days after onset, for 30 days after the last dose of study drug, until the subject is lost to follow-up (as defined in [Section 6.4.1](#)), or the subject withdraws consent, whichever occurs first. Serious adverse events (SAEs) will be reported up to 30 days after the last dose of study drug. A follow-up phone call will be made 30 days after the last dose of study drug for evaluation of any SAEs.
20. Study drug will be administered in the clinic on the morning of Day 1. Study drug will be administered on an outpatient basis on the evening of Day 1 through the morning of Day 26. Subjects will be instructed to bring all used empty bottles and unused study drug, with them to the end-of-study visit on Day 26.
21. Drug compliance will be assessed by capsule count.

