Subjects experiencing specified adverse events will have their dose adjusted.

A member of the study staff will contact any subject who is suspected of experiencing neuropsychiatric adverse events to determine the need for an unscheduled visit before further dose escalation may proceed.

Though amendments 4 and 5 of the protocol were executed, no subjects enrolled under these amendments. Amendment 4 changed the target population and replaced the use of ambulatory electroencephalograms (EEG) with standard multi-lead video EEGs. Amendment 5 removed dosing

on Day 27. Since no subjects enrolled under these amendments, this schedule of assessments below and the data included in listings will be presented based on amendment 3.

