16. A single lead EEG will be bipolarly recorded for 5 days using a wearable EEG patch (Epitel device). The EEG recording will be centrally evaluated by a qualified rater. Subjects will be trained in the use of the device by site personnel and will replace the EEG patch every 7 days. Subjects will receive the device at screening. On Days 8 and 20, the nurse who conducts the home visit will check positioning of the device. The device will be returned on the Day 26 clinic visit. This assessment is based on device availability.
17. The "lifetime" version of the C-SSRS will be used at screening, and the "since last visit" version will be completed at all other visits.
18. The UM-PDHQ is a 20-item clinician-administered questionnaire that quantitatively and qualitatively assesses hallucinations. The UM-PDHQ will be completed for any subject who reports hallucinations.
19. All AEs, irrespective of the relatedness to the study drug, will be captured from the time the ICF is signed through the EOS visit. All AEs should be followed until resolution, for 30 days after onset, for 30 days after the last dose of study drug, until the subject is lost to follow-up, or the subject withdraws consent, whichever occurs first. Serious adverse events (SAEs) will be reported up to 30 days after the last dose of study drug. A follow-up phone call will be made 30 days after the last dose of study drug for evaluation of any SAEs.
20. Concomitant medications and adverse events will be recorded by the visiting nurse on Days 8 and 20.

21. Study drug will be administered in the clinic on the morning of Day 1 and Day 26. Study drug will be administered on an outpatient basis on the evening of Day 1 and Day 26 and on the morning of Day 27.
22. Drug compliance will be assessed by a remote mobile technology monitoring application (AiCure).
23. Evaluation of drug compliance and dosing accuracy will be assessed by the visiting nurse.
24. Subjects will return all remaining study drug (including empty bottles) to the site via a prepaid mailer.

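### The SAP's table rule can leave out pretreatment adverse events that worsen on treatment, although its own definition counts them as treatment-emergent

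*Protocol*

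**What the plan says.** **Treatment emergence.** Protocol 10.2.1 and SAP 3.3.7 define TEAEs in the same two limbs: events that occur in the treatment period, and events already present that increase in intensity during it. TEAEs head the list of primary endpoints in protocol 3.3.1 and SAP 5.3.1. AEs are recorded from signature of consent, and screening can last up to 28 days, so records that begin before dosing are expected.

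SAP 5.3.2.3 sets the table rules. Any AE with a start date before study treatment is left out of the tables and shown in the listings. AEs are allocated to a CX-8998 dose by start date. Treatment emergence is settled by reference to SAP 3.3.5, whose criteria use start and stop dates only.

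**Length of follow-up (minor).** Protocol 10.2.3 ends follow-up at the earliest of several limits, one being "30 days from onset; or". Table 3 footnote 19 agrees: "All AEs should be followed until resolution, for 30 days after onset, for 30 days after the last dose of study drug". The SAP's amendment 3 schedule carries the same limit: "for 30 days after onset, for 30 days after the last dose of study drug, until the subject is lost to follow-up". Protocol 4.6, in text printed twice below Table 2, has no onset limit: "All AEs should be followed for resolution or for 30 days from the last dose of study drug, whichever is shorter".

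**The concern.** The SAP includes worsened pretreatment events by definition and removes them by its table rule. The definition matters because it lets a drug effect on an existing complaint count as a safety finding. If the table rule is followed literally, that part of the primary endpoint is not tabulated.

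The exclusion is worded for the tables in general. It therefore reaches the overall, severity, related and by-dose summaries (14.3.1.1 to 14.3.1.4) and the serious, discontinuation and special-interest summaries (14.3.2.1 to 14.3.2.3). The dose rule adds a second gap: even if such an event were kept, its start date falls before any dose level. In a titration study the by-dose table is where a reader would look for a worsening at the higher doses.

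**Working it through.** The main point is a comparison of texts. The plan gives no figure to reproduce.

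**Step 1: trace one record.** Take, for illustration, a mild AE that starts on Day -6 and becomes moderate on Day 15, when the schedule gives 8 mg BID (Days 15 to 20).

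| Rule | Worsening kept under the original record | Worsening entered as a new record |
|---|---|---|
| SAP 3.3.7 definition | TEAE (second limb) | TEAE |
| SAP 3.3.5 date criteria | Start is before first dose and not missing, so none of the three criteria is met | Start is after first dose, so treatment-emergent |
| SAP 5.3.2.3 exclusion | Out of the tables; in the listing (16.2.7) only | In the tables |
| SAP 5.3.2.3 dose allocation | Day -6: no dose level | Day 15: 8 mg BID |

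The two columns describe the same clinical event. Only the recording convention differs, and neither document states one.

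**Step 2: size.** The documents give no AE rate, so the number of such events cannot be calculated. For one subject whose only qualifying event in a table row is dropped, the loss is 1/N. With N = 15 (SAP 3.1, a maximum), 1/15 = 0.067, or about 6.7 percentage points; with fewer subjects it is larger. If the subject has another event in the same row, that row's incidence does not change.

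**Step 3: the follow-up wording.** Take an unresolved AE with onset on Day 1 and last dose on Day 26, and read 4.6 as covering all AEs:
- 10.2.3 and footnote 19: Day 1 + 30 = Day 31.
- 4.6: Day 26 + 30 = Day 56.
- Difference: 56 - 31 = 25 days of required follow-up.

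The difference shrinks as onset approaches the last dose, and it is zero for onset on Day 26.

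**The case against.** **On the main point.** The SAP refers readers to the eCRFs for details of data collection, and these are not available here. If sites enter a worsening as a new AE with its own date, nothing is lost. The SAP 3.3.5 criteria are also framed as additions for missing dates, so they need not displace the 3.3.7 definition. A sensible programmer might read the exclusion as aimed only at AEs that are not treatment-emergent. Affected events would in any case stay in the listings, for at most about 15 subjects. All of this stands as a limit on the consequence. It does not remove the contradiction, because the exclusion covers every earlier start date and no text requires a new record.

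**On follow-up length.** A reader might infer that the protocol leaves follow-up ungoverned and that TEAEs are lost as a result. The documents do not support that, for these reasons:
- Sections 6.4.1 and 7.2.8 both send the reader to 10.2.3. This is not express precedence over 4.6, but it points one way.
- The sentence in 4.6 follows one about subjects who stop treatment for AEs and can be read as limited to them. Onset may then lie close to the last dose, where the difference is small.
- It is tempting to add that the onset limit lets follow-up of screening AEs lapse during titration (onset on Day -28 reaches it on Day 3). That needs onset early in a long screening period, and screening is only up to 28 days.
- Routine AE collection runs to Day 33 under either rule.
- The open-ended duty in 10.2.3 ("treated and followed up until the symptoms or values return to normal or acceptable levels, as judged by the investigator and the sponsor") and the one in 6.4.1 ("the subject should remain under the supervision of the investigator until the medical issue is resolved or otherwise declared stable") can be read as medical care, and longer follow-up is never forbidden.
- The SAP presents the amendment 3 schedule, explaining: "Since no subjects enrolled under these amendments". The amendments meant are 4 and 5, which the supplied protocol text matches. The amendment 3 wording of 4.6 is not shown.

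**Conclusion.** The SAP contradicts itself on worsened pretreatment AEs and should be corrected. The contradiction lies within the SAP, so it holds whichever amendment subjects enrolled under. The supportable claim is that qualifying events *may* be left out of the primary-endpoint tables. That they *are* left out is a stronger reading, which would require knowing that worsening stays under the original record. On that condition, such an event is absent from every AE table and has no dose level. The possible size is about 6.7 percentage points per subject at N = 15, with the number of subjects unknown.

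The difference between 4.6 and 10.2.3 is a wording inconsistency about the minimum length of follow-up. It changes no stated result, and choosing the longer limit over the shorter is largely a preference.

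**What to change.** **SAP, either option:**
1. In 5.3.2.3, confine the table exclusion to pretreatment AEs that do not worsen after first dose. Add a matching worsening criterion to 3.3.5, and allocate worsened events to dose by date of worsening.
2. Require a worsening to be entered as a new AE record with its own start date. The existing date and dose rules then work unchanged.

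The first option costs a few sentences in the SAP, plus a data query for any worsening that was not dated. The second costs one line in the eCRF completion guide. Neither needs a new visit, and the SAP change needs no protocol amendment.

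**Protocol, low priority:** use one follow-up rule in 4.6 (both printings), 10.2.3 and Table 3 footnote 19. Aligning 4.6 to 10.2.3 is simplest, because two sections already point there and the SAP footnote agrees. If the longer last-dose limit is preferred, change the SAP footnote too and keep the onset limit for subjects never dosed, such as the screen failures in exclusion criterion 17 ("fewer than 3 typical absence seizures during the baseline video-EEG (considered to be screen failures"), who have no last dose to count from. The Day 57 call, which 7.2.10 limits to SAEs, would then need a question on unresolved AEs.
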